4.10 Subgroup analysis

Based on the data availability, ORR, DoR, DCR, PFS, and OS of Phase 2a arms might be analysed with following subgroups:

- Number of prior anti-cancer therapy: 0, 1, 2, 3, 4, ≥ 5 . Therapy setting of 'adjuvant', 'neo-adjuvant', 'maintenance' will be excluded from the number of prior anti-cancer therapy
- Number of lesions in liver at baseline: 0, 1, ≥ 2
- Baseline sum of target lesion: ≤ 100 mm, > 100 mm
- Baseline absolute lymphocyte count (ALC): $\leq 10^3/\mu\text{L}$, $> 10^3/\mu\text{L}$
- Age (year): < 65 , ≥ 65 to < 75 , ≥ 75
- Location of CPI naïve R/R MSS-CRC (Rectum, Colon, Other)

4.11 Safety Analysis

Safety analysis will be summarized by Phase 2 arms and by dose group for dose Phase 1b based on safety analysis set unless otherwise specified.

For safety shift tables, schedule and unscheduled measurements up to 30 days after last dose date will be included in worst postbaseline results derivation.

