## **6.6. Duration of Follow-Up and End of Study**

The active study will end when the last subject completes the 90-day Safety Follow-up visit, approximately 2 years after enrollment.

End of treatment (EOT) visit should be performed within approximately 7 days after disease progression determination, treatment discontinuation, or immediately before initiation of any other cancer therapy, whichever is earlier.

Safety Follow-up visit should be performed 30 ( $\pm$  7) days and 90 ( $\pm$  7) days after the last administration of either agent.

Subjects who complete all 35 cycles of treatment or permanently discontinue study treatment for reasons other than objective disease progression confirmed by RECIST 1.1 and iRECIST should continue to have RECIST scans performed every 9 weeks ( $\pm$  7 days), at the investigative site or locally, up to one year after discontinuation of study treatment. Standard of care disease assessments will be collected until the start of a new anticancer treatment, disease progression, pregnancy, death, withdrawal of consent or end of study, whichever occurs first.

After disease progression or start of new anticancer treatment, subjects will be followed for survival every 90 days ( $\pm$  7 days) until death, lost to follow-up, withdrawal of consent or end of the study, whichever occurs first. Survival follow-up can be done either by in-person visit or by telephone assessment.

Subjects removed from study for unacceptable AE(s) will be followed until resolution or stabilization of the AE; in addition, the subjects will be followed for disease status and overall survival, as described above.

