#### 11.3.1. Time Period and Frequency for Collecting AE, SAE and Other Reportable Safety Event Information

- All AEs, SAEs and other reportable safety events that occur after the consent form is signed but before treatment /allocation must be reported by the investigator, if the event causes the subject to be excluded from the study or is the result of a protocol-specified intervention, including but not limited to washout or discontinuation of usual therapy, diet, or a procedure.
- All AEs from the time of treatment/allocation through 30 days following cessation of study treatment or starting of new anticancer therapy, whichever is earlier, must be reported by the investigator.
- All AEs meeting serious criteria, from the time of treatment/ allocation through 90 days following cessation of study treatment or initiation of new anticancer therapy, whichever is earlier, must be reported by the investigator.
- All pregnancies and exposure during breastfeeding, from the time of treatment/ allocation through 90 days following cessation of study treatment or initiation of new anticancer therapy, whichever is earlier, must be reported by the investigator.
- Additionally, any SAE brought to the attention of an investigator at any time outside of the time period specified above must be reported immediately to the Sponsor if the event is considered to be drug-related.

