2.4 Study Visits

Study visits in EDC datasets include screen, C1D1, C1D2 C1D8, C2D1, C2D8, C2D15, C3D1, C3D8, C4D1, C5D1, C6D1, C6D15, ..., CnD1, End of Treatment, safety follow ups, survival follow ups as well as unscheduled. The unscheduled study visits will not be recalculated for the analysis by visit, but the unscheduled visit values will be considered in the summary of worst change from baseline.

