4.11.2 Adverse Events

AE will be coded using MedDRA version 27.1 and graded using the NCI-CTCAE version 5.0.

A TEAE is any AE that starts on/after the first day of study treatment or that worsens on/after the first day of study treatment, and up to 30 days (90 days for serious adverse events [SAEs]) after the date of last dose of study drugs, or initiation of new anticancer therapy, whichever is earlier.

For the purpose for regulatory reporting, relationships of “definite”, “probable” and “possible” to study drug as assessed by the investigator will be defined as related to study treatment. Missing relationship will not be imputed.

Adverse events of special interest (AESIs) in NT-I7 are defined in protocol section 11.4. Events of clinical interest (ECI) in pembrolizumab are defined in protocol section 11.6.

An overall summary of TEAEs using frequencies and percentages of subjects will be presented based on the following categories:

- TEAEs
- NT-I7-related TEAE
- Pembrolizumab-related TEAE
- Either NT-I7 or pembrolizumab-related TEAE
- TEAEs with Grade 3 or higher
- NT-I7-related TEAE with Grade 3 or higher
- Pembrolizumab-related TEAE with Grade 3 or higher
- Either NT-I7 or pembrolizumab-related TEAE with Grade 3 or higher
- Serious TEAE
- NT-I7-related serious TEAE
- Pembrolizumab-related serious TEAE
- Either NT-I7 or pembrolizumab-related serious TEAE
- TEAEs leading to NT-I7 interrupted/held
- TEAEs leading to NT-I7 dose reduced
- TEAEs leading to NT-I7 permanently withdrawn
- TEAEs leading to pembrolizumab interrupted/held
- TEAEs leading to pembrolizumab permanently withdrawn
- TEAEs leading to discontinuation from the study
- AESI in NT-I7
- ECI in pembrolizumab
- TEAEs considered injection site reaction (ISR)
- TEAEs considered infusion-related reactions (IRR)
- TEAEs leading to death

The above events will be tabulated by SOC and PT. SOC will be sorted by descending frequency and then alphabetically for ties. Within each SOC, PT will also be sorted by descending frequency and then alphabetically for ties, by the overall number of subjects in Phase 1b/Phase 2a total. If a PT is reported more than once for a subject, the subject will only be counted once in the incidence for that PT.

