4.11.3 Clinical Laboratory Evaluation

Hematology, serum chemistry, coagulation, thyroid function test, and urinalysis tests are listed in table 6.

Table 6 Clinical Laboratory Tests

Chemistry	Hematology
Alanine aminotransferase (ALT)/ serum glutamate pyruvic transaminase (SGPT)	Red blood cell (RBC); Erythrocyte
Albumin	Hemoglobin
Alkaline phosphatase (ALP)	Hematocrit
Aspartate aminotransferase (AST); serum glutamic oxaloacetic transaminase (SGOT)	White blood cell (WBC); Leukocytes
Bicarbonate	Neutrophils (Absolute)
Blood urea nitrogen (BUN)	Neutrophils band form (Absolute)
Calcium	Lymphocytes (Absolute)
Chloride	Monocytes (Absolute)
Creatinine	Eosinophils (Absolute)
Direct bilirubin	Basophils (Absolute)
Glucose	Neutrophils/Leukocytes (%)
Indirect bilirubin	Neutrophils band form/Leukocytes (%)
Lactate dehydrogenase (LDH)	Lymphocytes/Leukocytes (%)
Magnesium	Monocytes/Leukocytes (%)

Phosphate Potassium Protein Sodium Total bilirubin (TBL) Urate (Uric Acid) Urea	Eosinophils/Leukocytes (%) Basophils/Leukocytes (%) Platelets
Coagulation	Urinalysis
Activated partial thromboplastin time (aPTT) International normalized ratio (INR) Prothrombin time (PT)	pH Specific Gravity Bilirubin Glucose Ketones Leukocyte esterase Nitrite Occult blood Protein Urobilinogen
Thyroid function test	
Thyroid stimulating hormone (TSH) Thyroxine, free (Free T4) Triiodothyronine (Total T3) Triiodothyronine, free (Free T3)	

Absolute value, change from baseline, and percentage change from baseline for continuous parameters (analytes) of hematology, serum chemistry, coagulation, and thyroid function tests will be summarized by visit and DLs/arm in each phase using descriptive statistics (mean, median, STD, minimum, maximum, and number of subjects).

Baseline and post-baseline hematology, serum chemistry, and coagulation tests will be classified as Grade 0, Grade 1, Grade 2, Grade 3, and Grade 4 based on CTCAE v5.0. Shift of these tests from baseline CTCAE grade to the worst postbaseline CTCAE grade will be presented by DLs/arm in each phase using the number and percentage of subjects at each shift category. If applicable, some laboratory tests have two CTCAE grade directions: hypo and hyper, where both directions will be presented in the shift table.

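### The SAP's worst post-baseline window for safety shift tables does not stop at new anticancer therapy, although the TEAE window does, so values taken after an early switch can enter the shift tables with no matching TEAE

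*SAP*

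**What the plan says.** **Shift tables.** SAP 4.11: "For safety shift tables, schedule and unscheduled measurements up to 30 days after last dose date will be included in worst postbaseline results derivation". SAP 4.11.3 builds the laboratory tables on that value: "Shift of these tests from baseline CTCAE grade to the worst postbaseline CTCAE grade will be presented by DLs/arm in each phase". SAP 4.11.6 plans the same kind of table for ECOG status. On unscheduled visits, SAP 2.4 says that "the unscheduled visit values will be considered in the summary of worst change from baseline". None of these sections mentions new anticancer therapy.

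**Adverse events.** The TEAE definition in SAP 4.11.2 runs to 30 days (90 for SAEs) "after the date of last dose of study drugs, or initiation of new anticancer therapy, whichever is earlier". Protocol 11.3.1 sets the AE reporting period in the same way: "through 30 days following cessation of study treatment or starting of new anticancer therapy, whichever is earlier".

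**Visits.** Under protocol 6.6 the End of Treatment visit falls within about 7 days of progression or discontinuation, or "immediately before initiation of any other cancer therapy, whichever is earlier". After that, "Safety Follow-up visit should be performed 30" (± 7) and 90 (± 7) days from the last administration of either agent. The protocol 7.4 schedule includes blood count, serum chemistry and performance status at safety follow-up.

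**Liver categories.** SAP 4.11.3 also tabulates worst post-baseline AST, ALT, bilirubin and ALP categories, including the combined row for potential drug-induced liver injury. It gives no end date for them and does not call them shift tables.

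**The concern.** Two safety summaries of the same subjects use different end points, and the SAP does not say why. SAP section 6, which lists departures from the protocol analysis, is silent on it. The SAP does treat new therapy as a cut elsewhere: in the TEAE definition, and in the DoR and PFS censoring rules (SAP Tables 4 and 5).

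Suppose a subject starts next-line therapy soon after the last dose and then has a low count or raised transaminase by day 30. That value can fill a high-grade shift cell for NT-I7 plus pembrolizumab. The same finding, if reported as an adverse event starting after the switch, would not be treatment-emergent. The laboratory and AE tables would then disagree for a reason that the tables do not show. The arms are small and have no control group, so a single subject is visible in a cell.

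**Working it through.** The plan gives no figure to reproduce. The check is a comparison of windows, followed by the size of one affected subject.

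**1. Windows side by side**

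| Item | Upper limit | Stops at new therapy? |
|---|---|---|
| Worst value for shift tables (SAP 4.11) | 30 days after last dose | No |
| TEAE (SAP 4.11.2) | 30 days, 90 for SAEs | Yes |
| AE reporting (protocol 11.3.1) | 30 days, 90 for SAEs | Yes |
| AE reporting (protocol 11 introduction; 7.4 footnote 9) | 30 days, or the 30-day visit; footnote 9 adds SAEs to the 90-day visit | No |
| Worst liver categories (SAP 4.11.3) | Not stated | Not stated |

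SAP 2.4, 4.11.3 and 4.11.6 add no stop for shift tables.

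**2. Which values can get in**

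Take the last dose in SAP 4.11 to be the last administration of either agent, as protocol 6.6 does for the visits.

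- End of Treatment values should precede new therapy, so they are clean if the visit is timed as planned.
- The 30-day visit can fall from day 30 − 7 = 23 to day 30 + 7 = 37. Draws on days 23 to 30 are inside the window. Draws on days 31 to 37 are already outside it.
- Unscheduled values count up to day 30.

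An affected value therefore needs three things: new therapy started before day 30, a later measurement by day 30, and a grade worse than any earlier post-baseline grade for that subject.

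**3. Size of one such subject**

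Change in a shift cell = 100 / n percentage points.

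- n = 30 (maximum enrolled per Phase 2a arm): 100/30 = 3.3
- n = 25 (planned evaluable per Simon arm): 100/25 = 4.0
- n = 10 (Biomarker Cohort): 100/10 = 10.0
- n = 6 (maximum per Phase 1b dose level): 100/6 = 16.7

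**4. How often**

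The documents give no rate of switching within 30 days. As an illustration only, let q be the share of subjects who both switch in the window and get a worse grade from it. The chance of at least one in an arm is 1 − (1 − q)^n. At n = 25:

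- assumed q = 1%: 1 − 0.99^25 = 22%, with 25 × 0.01 = 0.25 subjects expected
- assumed q = 9%: 1 − 0.91^25 = 91%, with 25 × 0.09 = 2.25 subjects expected

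The width of that range shows that the plan does not determine the frequency.

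**The case against.** The best defence is that a wide window is the cautious choice for safety. Protocol 8.2 says that immune-related events may appear several months after the last pembrolizumab dose. SAP 4.8 adds 43 to the difference between last and first NT-I7 dose dates, which counts exposure to 42 days beyond the last dose. A value on day 28 may still reflect study drug even if new therapy has begun. This stands as a real cost of the fix. It does not explain why the SAP cuts TEAEs at new therapy and leaves shift tables open. If the wider window is intended, the SAP should say so and mark the values taken after a switch.

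Other points also stand in part:

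- The introduction to protocol section 11 and footnote 9 of the schedule collect AEs to about 30 days with no therapy stop. An AE after the switch may therefore still appear in the listing of all AEs, without the TEAE flag.
- It is arguable whether the 30-day visit takes place after a switch. Protocol 6.6 moves subjects to survival follow-up after new treatment starts, while footnote 28 starts survival follow-up only after the 90-day safety visit. No text expressly waives the 30-day visit, and none expressly requires it after a switch.
- SAP 4.11.3 lists all laboratory values, so an affected subject can be traced by hand.
- The liver categories are not named as shift tables. The gap there is an unstated window, not a demonstrated mismatch.

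**Conclusion.** The omission is certain from the text. Its effect is possible but not quantified. Followed as written, SAP 4.11 can place a value taken after an early switch in a shift cell while the matching event is not a TEAE. Each such subject moves a cell by 3.3 to 16.7 points, depending on the size of the group. The TEAE tables, DLTs and ORR are untouched. This is a minor reporting inconsistency that is worth closing because closing it is cheap.

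A reader might infer more than this, and the documents do not support it:

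- *That next-line toxicity will be reported as study-drug toxicity.* Shift tables are descriptive and assign no cause, and the route is narrow (step 2 of the working).
- *That the distortion is large.* If 10% to 30% of an arm switched to cytotoxic therapy within 30 days and 20% to 40% of those then had a Grade 3-4 count, the product would be 2% to 12%, or 0.6 to 3.6 of 30 subjects. Both rates are assumptions. The product also ignores subjects already at that grade, who add nothing to a worst-grade table. For lymphocytes, early falls are expected on NT-I7 (protocol 6.2.1, note). Inclusion criterion 3 admits subjects who have progressed after all available beneficial therapy, are intolerant, or refuse standard treatment. That gives no basis for assuming frequent early cytotoxic starts.
- *That fast-progressing arms are hit hardest.* This is plausible, but nothing in the documents shows it.

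**What to change.** In SAP 4.11, end the worst post-baseline window at the earlier of 30 days after last dose or start of new anticancer therapy, as SAP 4.11.2 does for TEAEs. State in SAP 4.11.3 that the same window applies to the worst post-baseline liver categories. Keep later values in the laboratory and ECOG listings with a flag showing that they follow new therapy.

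The cost is a sentence in each section and one programming condition. The new-therapy start date is already needed for TEAEs and for DoR and PFS censoring. The downside is that some values within 30 days of last dose that could still reflect late immune effects of study drug move from the summary tables to the flagged listings, where they remain open to review.

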4.11.1 Dose-limiting Toxicities

All toxicities will be graded using NCI-CTCAE Version 5.0. For the purpose of this study, a DLT is any event attributed to NT-I7 and/or to pembrolizumab and occurring during the DLT period of first 21 days.

DLT is defined as any AE occurring within the first 21 days (i.e., Cycle 1, Day 1 through Day 21), that is considered to be at least possibly, probably, or definitely related to the study treatment (NT-I7 and/or pembrolizumab) per the investigator, and that meets at least one of the non-hematologic or hematologic criteria listed below.

- Grade 4 non-hematologic toxicity (not laboratory).
- Grade ≥ 3 diarrhea, nausea, or vomiting without use of anti-emetics or anti-diarrheal per standard of care
- Grade ≥ 3 rash, lasting ≥ 5 days
- Grade 4 neutropenia, lasting ≥ 5 days
- Febrile neutropenia Grade 3 or Grade 4:
 - Grade 3 is defined as absolute neutrophil count (ANC) $< 1000/\text{mm}^3$ with a single temperature of > 38.3 degrees C (101 degrees F) or a sustained temperature of ≥ 38 degrees C (100.4 degrees F) for more than 1 hour

- Grade 4 is defined as ANC < 1000/mm³ with a single temperature of > 38.3 degrees C (101 degrees F) or a sustained temperature of ≥ 38 degrees C (100.4 degrees F) for more than 1 hour, with life-threatening consequences and urgent intervention indicated.
- Other Grade 4 hematologic toxicity lasting ≥ 7 days, except thrombocytopenia:
 - Grade 4 thrombocytopenia of any duration
 - Grade 3 thrombocytopenia associated with clinically significant bleeding

Note: Peripheral lymphocytopenia after the first NT-I7 injection is not a sign of toxicity; it reflects the lymphocytes “homing effect” of NT-I7. Lymphocyte counts usually come back to baseline 5 to 7 days after the first injection.

- Any non-hematologic AE ≥ Grade 3 in severity should be considered a DLT, with the following exception: Grade 3 fatigue lasting ≤ 3 days.; without use of corticosteroids or anti-inflammatory agents per standard of care.
- Any Grade 3 or Grade 4 non-hematologic laboratory value if:

- Clinically significant medical intervention is required to treat the subject, or
- Abnormality leads to hospitalization, or
- The abnormality persists for > 1 week, or
- The abnormality results in potential Drug-induced Liver Injury (DILI) as defined by Hy's Law.

Exceptions: Clinically nonsignificant, treatable, or reversible laboratory abnormalities including liver function tests, uric acid, etc.

- Other Grade ≥ 3 clinical laboratory abnormalities must be reversible to ≤ Grade 1 within 72 hours with outpatient care and/or monitoring AND must not be considered clinically significant by the treating physician to be excluded from the definition of DLT.
- Prolonged delay (> 2 weeks) in initiating Cycle 2 due to treatment-related toxicity.
- Any treatment-related toxicity that causes the subject to discontinue treatment during Cycle 1.
- Grade 5 toxicity.

DLTs in each cohort of dose escalation (Phase 1b) will be coded using MedDRA version 27.1 and will be summarized by SOC and PT using DLT analysis set.

DLTs will also be displayed in a data listing.

4.11.2 Adverse Events

AE will be coded using MedDRA version 27.1 and graded using the NCI-CTCAE version 5.0.

A TEAE is any AE that starts on/after the first day of study treatment or that worsens on/after the first day of study treatment, and up to 30 days (90 days for serious adverse events [SAEs]) after the date of last dose of study drugs, or initiation of new anticancer therapy, whichever is earlier.

For the purpose for regulatory reporting, relationships of “definite”, “probable” and “possible” to study drug as assessed by the investigator will be defined as related to study treatment. Missing relationship will not be imputed.

Adverse events of special interest (AESIs) in NT-I7 are defined in protocol section 11.4. Events of clinical interest (ECI) in pembrolizumab are defined in protocol section 11.6.

An overall summary of TEAEs using frequencies and percentages of subjects will be presented based on the following categories:

- TEAEs
- NT-I7-related TEAE
- Pembrolizumab-related TEAE
- Either NT-I7 or pembrolizumab-related TEAE
- TEAEs with Grade 3 or higher
- NT-I7-related TEAE with Grade 3 or higher
- Pembrolizumab-related TEAE with Grade 3 or higher
- Either NT-I7 or pembrolizumab-related TEAE with Grade 3 or higher
- Serious TEAE
- NT-I7-related serious TEAE
- Pembrolizumab-related serious TEAE
- Either NT-I7 or pembrolizumab-related serious TEAE
- TEAEs leading to NT-I7 interrupted/held
- TEAEs leading to NT-I7 dose reduced
- TEAEs leading to NT-I7 permanently withdrawn
- TEAEs leading to pembrolizumab interrupted/held
- TEAEs leading to pembrolizumab permanently withdrawn
- TEAEs leading to discontinuation from the study
- AESI in NT-I7
- ECI in pembrolizumab
- TEAEs considered injection site reaction (ISR)
- TEAEs considered infusion-related reactions (IRR)
- TEAEs leading to death

The above events will be tabulated by SOC and PT. SOC will be sorted by descending frequency and then alphabetically for ties. Within each SOC, PT will also be sorted by descending frequency and then alphabetically for ties, by the overall number of subjects in Phase 1b/Phase 2a total. If a PT is reported more than once for a subject, the subject will only be counted once in the incidence for that PT.

The following events will be tabulated by SOC, PT, and maximum CTCAE grade. SOC will be sorted by descending frequency and then alphabetically for ties. Within each SOC, PT will be sorted by descending frequency and then alphabetically for ties, by the overall number of subjects.

- TEAEs
- NT-I7 -related TEAE
- Pembrolizumab-related TEAE
- Either NT-I7 or pembrolizumab-related TEAE

Summaries of events by decreasing frequency of PT include:

- TEAEs
- NT-I7 Related TEAE

Confidential

- Pembrolizumab Related TEAE
- Serious TEAE
- NT-I7 Related Serious TEAE
- Pembrolizumab Related Serious TEAE

If a PT is reported more than once for a subject, the subject will only be counted once in the incidence for that PT.

The following listings will be provided:

- All AEs (flag TEAE)
- SAEs (flag TEAE)
- TEAEs leading to NT-I7 interrupted/held
- TEAEs leading to NT-I7 permanently withdrawn
- TEAEs leading to NT-I7 dose reduced
- TEAEs leading to pembrolizumab interrupted/held
- TEAEs leading to pembrolizumab permanently withdraw
- AESI in NT-I7
- ECI in pembrolizumab
- TEAEs leading to death
- TEAEs considered ISR
- TEAEs considered IRR
- TEAEs leading to death

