Prior medications – Record all medications (prescription and over-the-counter [OTC]) taken within 30 days of Screening visit. Concomitant medications – Enter all medications (prescription and OTC) taken between 7 days prior to Cycle 1, Day 1 through the Safety Follow-up visit.

Full physical exam is required during Screening, Day 1 of every cycle, End of Treatment, and Safety Follow-up visits. A directed physical exam may be performed on other days as clinically indicated.

Performance status must be assessed per ECOG Performance Scale criteria.

Vitals (blood pressure, heart rate, respiratory rate, temperature) to be collected in a standardized manner in a sitting position after the subject has rested comfortably for ~5 minutes. On the odd-numbered cycles (pembrolizumab and NT-I7), vitals need to be obtained within 60 minutes prior to the start of the pembrolizumab infusion AND repeated after the completion of the pembrolizumab infusion, but before the NT-I7 injection. On the even-numbered cycles (pembrolizumab only), vitals need to be obtained within 60 minutes prior to the start of the pembrolizumab infusion.

Height is measured on the first visit during Screening only.

All AEs, including those meeting serious criteria, from the time of consent through the 30-day safety follow-up visit, and AEs meeting serious criteria only from 30 days following cessation of study treatment to 90-day safety follow-up visit. See Section 11 for additional details on reporting of AEs.

Duplicate EKG, at least 5 minutes apart, and serum cardiac enzyme levels (Troponin (TnI or TnT) and CK-MB) must be obtained at Screening, C1D1, every 4 cycles (i.e., C5D1, C9D1,..), and End of Treatment. A patient should be assessed by a PI or a local cardiologist to determine if the EKG and the serum cardiac enzyme levels are clinically significant. If either is found to be clinically significant, see footnote 30.

Hematology includes complete blood count (CBC) with differential, including but not limited to red blood cell (RBC) count, hemoglobin, hematocrit, white blood cell (WBC) count with differential (neutrophil count including lymphocyte, monocyte, eosinophil, basophil counts and bands), absolute neutrophil count (ANC), and platelet count.

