## 8.2. Dose Modification of Pembrolizumab

The toxicity of pembrolizumab could be accentuated by administration of NT-I7 and the component attributable to pembrolizumab and NT-I7 will be difficult if not impossible to sort out. Thus, the management of pembrolizumab will be used for the treatment of any AE. NT-I7 treatment will be discontinued when pembrolizumab must be **permanently discontinued**.

AEs associated with pembrolizumab exposure may represent an immune-related response. These irAEs may occur shortly after the first dose or several months after the last dose of pembrolizumab treatment and may affect more than one body system simultaneously. Therefore, early recognition and initiation of treatment is critical to reduce complications. Based on existing clinical study data, most irAEs were reversible and could be managed with interruptions of pembrolizumab, administration of corticosteroids and/or other supportive care. For suspected irAEs, ensure adequate evaluation to confirm etiology or exclude other causes. Dose modification and toxicity management guidelines for irAEs associated with pembrolizumab are provided in [Table 4](#).

When study interventions are administered in combination, attribution of an adverse event to a single component is likely to be difficult. Therefore, while the investigator may attribute a toxicity event to the combination, to NT-I7 alone, or to pembrolizumab alone, for adverse events listed in [Table 4](#), both interventions must be held according to the criteria in .

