### 11.3.2. Expedited Reporting Guidelines

Use the study protocol number and the protocol-specific subject ID assigned during study registration on all reports. Progression of the cancer under study is not considered an adverse event unless it results in hospitalization or death.

**Note: A death occurring within 90 days of the last administration of study agent requires both routine and expedited reporting, regardless of causality. Attribution to treatment or other cause must be provided.**

Death due to PD should be reported as **Grade 5 “Malignant neoplasm progression”** to be coded under the system organ class (SOC) “Neoplasms benign, malignant and unspecified (incl cysts and polyps)”. Evidence that the death was a manifestation of underlying disease (e.g., radiological changes suggesting tumor growth or progression; clinical deterioration associated with a disease process) should be submitted.

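### Final adverse event tables omit drug-related SAEs that begin after new anticancer therapy or after day 90, and 90-day deaths from events that begin after a switch, although the protocol requires both to be reported

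*SAP*

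**What the plan says.** SAP 4.11.2 calls an event treatment-emergent if it starts or worsens on or after the first treatment day, with an upper limit of 30 days, or 90 for a serious event, "after the date of last dose of study drugs, or initiation of new anticancer therapy, whichever is earlier". It makes no exception for events judged related to study drug. The overall summary, the tables by system organ class and preferred term, the maximum-grade tables and the frequency tables are built on this definition. They include related serious TEAEs and TEAEs leading to death.

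Protocol 11.3.1 sets the same routine window for serious events, "through 90 days following cessation of study treatment or initiation of new anticancer therapy, whichever is earlier, must be reported by the investigator". For events considered drug-related it then goes further: "any SAE brought to the attention of an investigator at any time outside of the time period specified above must be reported immediately". Protocol 11.3.2 adds: "A death occurring within 90 days of the last administration of study agent requires both routine and expedited reporting, regardless of causality". That clause has no cut at new therapy. Protocol 11.3.3 requires events reported expeditiously to be entered in the routine study data as well, so these events should be available for analysis.

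**The concern.** The protocol asks sites for two kinds of event that the SAP's counting rule leaves out. Both bear on late toxicity, which the protocol expects; of immune-related events it says "These irAEs may occur shortly after the first dose or several months after the last dose of pembrolizumab treatment". Protocol 2.4.1.3 adds myocarditis as a potential NT-I7 risk after two fatal events in combination with checkpoint inhibitors, and says a causal role for NT-I7 cannot be ruled out. Adverse event incidence is a Phase 1b primary endpoint and a Biomarker Cohort secondary endpoint.

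The related-serious and fatal event rates in the study report could therefore be lower than the collected data support. A listing shows the individual case but gives no rate. Overall survival counts the death but shows neither cause nor relatedness.

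**Working it through.** The plan states no figure to reproduce. The check compares the reporting rules with the counting rule, case by case.

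| Case | Reportable under the protocol? | TEAE under SAP 4.11.2? | Where it appears in the final outputs |
|---|---|---|---|
| Related SAE, onset after a switch | Yes, 11.3.1 any-time clause | No | All-AE and SAE listings only |
| Related SAE, onset after day 90, no switch | Yes, same clause | No | Same listings only |
| Death within 90 days, fatal event began after a switch | Yes, 11.3.2 | No | Listings; the death counts in OS |
| Death after a switch, fatal event began before it | Yes, if within 90 days | Yes, onset is inside the window | Can stay in TEAEs leading to death |
| Unrelated non-fatal SAE, onset after a switch | No | No | Plan and protocol agree |

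The first three rows are the gap. The second shows that it does not depend only on switching therapy.

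**Effect of one omitted event.** Safety denominators are all treated subjects (SAP 3.1), with up to 30 per Phase 2a arm (SAP 1.4). The SAP plans counts and percentages for adverse events; the exact limits below are added to show what a reader could rule out.

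- Change in rate: 1/30 = 3.3 percentage points.
- 0/30, two-sided 95% Clopper-Pearson upper limit: 1 − 0.025^(1/30) = 11.6%.
- 1/30, upper limit: the p that solves (1 − p)^30 + 30p(1 − p)^29 = 0.025, which is 17.2%.
- Smaller groups move more: 1/6 = 16.7 points at a Phase 1b dose level of 6, and 1/10 = 10 points in a Biomarker Cohort of 10.

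**Days removed for one subject who switches.** The documents give no time to switch, so the switch day s after last dose is assumed. Days lost from the 90-day serious-event window = 90 − s:

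- s = 14: 76 days (84%)
- s = 30: 60 days (67%)
- s = 60: 30 days (33%)

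These are post-treatment days for one subject. They are not proportions of events lost.

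**The case against.** The strongest reply is that the SAP follows the protocol's own window. Protocol 11.3.1 ends routine SAE reporting at 90 days or new therapy, and SAP 4.11.2 repeats it. The any-time clause is passive: it covers what comes to an investigator's attention, so ascertainment after the window is incomplete, and keeping such reports out of incidence rates can be defended. This stands as a reason to keep the ordinary window and to label late counts carefully. It does not justify having no summary of related SAEs and 90-day deaths that sites must report.

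Some stronger readings are tempting but not supported:

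- *The events disappear from every safety output.* They do not. The all-AE and SAE listings flag TEAE status without filtering on it. Safety shift tables run to 30 days after last dose with no new-therapy cut (SAP 4.11). The interim list in SAP 5 names SAE without the TEAE prefix. The AESI listing also lacks that prefix.
- *All deaths after a switch are excluded.* Only those whose fatal event began after the switch are.
- *Footnote 9 of the Schedule of Assessments is a third contradiction.* It collects "AEs meeting serious criteria only from 30 days following cessation of study treatment to 90-day safety follow-up visit" without mentioning new therapy, but then refers to Section 11, which contains the cut.
- *Every related adverse event should become treatment-emergent.* Protocol 11.3.1 stops routine reporting of non-serious events at 30 days or new therapy, so such a rule would mix collected events with largely uncollected ones.

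**Conclusion.** The point holds for drug-related SAEs with onset after a switch or after day 90, and for deaths within 90 days of last dose from events with onset after a switch. Followed as written, SAP 4.11.2 leaves these out of the final adverse event incidence tables, so related-serious and fatal rates can only be understated. One omitted event in an arm of 30 costs 3.3 points and lowers the exact upper limit from 17.2% to 11.6%.

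The number of such events is unknown; it depends on switching times and late-event rates that the documents do not give. A reader might infer bias that differs between arms. That is possible, but it cannot be shown from the documents, and no between-arm safety comparison is planned. The gap is one of tabulation, since the events remain visible in listings. It is worth closing before the final analysis because the data are already required.

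**What to change.** In SAP 4.11.2, keep the present window for unrelated and non-serious events and make two additions:

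1. Count SAEs assessed as related to NT-I7 or pembrolizumab regardless of onset time or new anticancer therapy, either by extending the TEAE definition for these events or in a supplementary table. Showing onset as within the window, after a switch, or after day 90 keeps the late events distinguishable.
2. Add a table of all deaths within 90 days of last dose, by cause and relatedness, regardless of new therapy. This matches protocol 11.3.2. Splitting by cause keeps deaths from disease progression apart from the rest.

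The cost is a sentence and one or two tables. No new collection is needed: protocol 11.3.1 to 11.3.3 already require these events, and footnote 28 of the Schedule of Assessments records new anticancer treatments at survival follow-up. The downsides are slightly higher counts, mixed causality after a switch, and incomplete ascertainment of late events. A table footnote should state the last two.
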